### 3.2.2. Secondary COVID-19 and SARS-CoV-2 Infection Endpoints

The incidence of asymptomatic SARS-CoV-2 infection after mRNA-1273 vaccination in adult SOT recipients and healthy adult participants with negative SARS-CoV-2 at baseline will be evaluated by the following endpoints:

The incidence of asymptomatic SARS-CoV-2 infection among recipients of mRNA-1273 SARS-CoV-2 vaccine will be defined in participants with negative SARS-CoV-2 at baseline as:

- bAb levels against SARS-CoV-2 nucleocapsid protein negative (as measured by Roche Elecsys) at Day 1 that become positive (as measured by Roche Elecsys) counted starting 28 days after the second dose and 28 days after the third dose of vaccine, OR
- Positive reverse transcriptase polymerase chain reaction (RT-PCR) (central lab or local diagnostic tests) counted starting 14 days after the second and after the third dose of vaccine

The incidence of COVID-19 after vaccination with mRNA-1273 in SOT recipients and healthy participants will be evaluated by the following endpoints:

- First occurrence of COVID-19 starting 14 days after the second dose and after the third dose of vaccine, where COVID-19 is defined as symptomatic disease based on the following criteria:
  - The participant must have experienced at least TWO of the following symptoms: fever ( $\geq 38^{\circ}\text{C}/\geq 100.4^{\circ}\text{F}$ ), chills, myalgia, headache, sore throat, or new olfactory and taste disorder(s), OR
  - The participant must have experienced at least ONE of the following respiratory signs/symptoms: cough, shortness of breath or difficulty breathing, OR clinical or radiographical evidence of pneumonia, AND
  - The participant must have at least 1 nasopharyngeal (NP) swab, nasal swab, or saliva sample (or respiratory sample, if hospitalized) positive for SARS-CoV-2 by RT-PCR
- First occurrence of severe COVID-19 starting 14 days after the second dose and after the third dose of vaccine, where severe COVID-19 is defined as symptomatic COVID-19 AND any of the following:
  - Clinical signs indicative of severe systemic illness, respiratory rate  $\geq 30$  per minute, heart rate  $\geq 125$  beats per minute, oxygen saturation ( $\text{SpO}_2$ )  $\leq 93\%$  on room air at sea level, or partial pressure of oxygen ( $\text{PaO}_2$ )/fraction of inspired oxygen ( $\text{FIO}_2$ )  $< 300$  mm Hg, OR

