### 5.2. Analysis Population for Part A

All participants who are enrolled in Part A will be considered into analysis populations for Part A regardless of whether participants continue to Part B.

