## **6.5. COVID-19 and SARS-CoV-2 Infection Analysis**

For both Part A and Part B, the mITT Set (Part A/Part B) will be used for the analysis of COVID-19 and SARS-CoV-2 infection starting from 14 days after the second dose and third dose received for each participant group. The PP Set (Part A/Part B) may be used in the analyses as appropriate, unless otherwise specified.

**Baseline SARS-CoV-2 status and Pre-booster SARS-CoV-2 Status** is described in [Section 6.1](#). The serology test results based on Roche Elecsys assay at baseline, and the RT-PCR test results at baseline will be summarized by participant group.

Participants with pre-vaccination baseline positive or missing SARS-CoV-2 status will be excluded from the mITT Set (Part A) infection analysis.

Participants with pre-booster positive or missing SARS-CoV-2 status will be excluded from the mITT Set (Part B) infection analysis.

The post-baseline serology test results based on the Roche Elecsys assay and the RT-PCR test results will also be summarized by visit.

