### 6.5.2. Analysis of Infection Rates

For Part A and Part B, the number and percentage of subjects experiencing each of the infection events below will be summarized by participant group for the mITT Set:

- SARS-CoV-2 infection
- Asymptomatic SARS-CoV-2
- COVID-19
- Severe COVID-19
- Secondary case definition of COVID-19

For each of these summaries, the incidence rate (i.e. the infection rate) will be provided by participant group, calculated as the number of cases divided by the total person-time. The 95% CI of the incidence rate will be calculated using the exact method (Poisson distribution) and adjusted by person-time.

Person-time is defined as the total time from first dose of each part of the study (Part A or Part B) to the earliest of the following dates: date of event, dose date in next part, last date of study participation, censoring time, or efficacy data cutoff date.

For participants who are a case for symptomatic COVID-19, symptoms reported by these participants will be summarized.

For SARS-CoV-2 infection, asymptomatic SARS-CoV-2 infection, COVID-19, and severe COVID-19, the timeframe for the counting cases will begin at 14 days after the last planned dose and will differ by study arm:

- 2-dose unvaccinated without booster: from day 43 up to and including day 394,
- 3-dose unvaccinated without booster: from day 99 up to and including day 450,
- 3-dose previously vaccinated with Moderna COVID-19 vaccine without booster: from day 15 up to and including day 365.
- 2-dose unvaccinated with booster: from BD-Day 1 + 14 up to and including BD-Day 181.

Confidential

- 3-dose unvaccinated with booster: from BD-Day 1 + 14 up to and including BD-Day 181)
- 3-dose previously vaccinated with Moderna COVID-19 vaccine with booster: from BD-Day 1+ 14 up to and including BD-Day 181 .
- 3-dose previously vaccinated with mRNA or non-mRNA COVID-19 vaccine with booster: from BD-Day 1 + 14 up to and including BD-Day 181.

In addition, the COVID-19 and SARS-CoV-2 infection endpoints may be also analyzed by specimen types (i.e. NP swab, nasal swab, or saliva samples), calendar months, time periods, and all types of the diagnostic test (i.e., both RT-PCR results and other COVID-19 test results). The number and percentage of subjects experiencing COVID-19 may be summarized by specific variant groups. Listings of serum nAb and bAb levels against SARS-CoV-2, solicited ARs and unsolicited AEs will be provided for subjects infected by SARS-CoV-2.

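### The case-counting list in SAP 6.5.2 gives later-boosted participants no Part A window, contradicting SAP 5.2, SAP 6.5.1 and the section's own person-time rule

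*SAP*

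**What the plan says.** The Part A secondary endpoint in SAP 3.2.2, matching Protocol Table 1, is "First occurrence of COVID-19 starting 14 days after the second dose and after the third dose of vaccine". Severe COVID-19 and the RT-PCR arm of asymptomatic infection use the same start. None of them depends on whether the participant is boosted later.

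For SARS-CoV-2 infection, asymptomatic infection, COVID-19 and severe COVID-19, SAP 6.5.2 then states that "the timeframe for the counting cases will begin at 14 days after the last planned dose and will differ by study arm". Its list has two kinds of row.

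- Arms without a booster get Part A windows. The two-dose row reads "2-dose unvaccinated without booster: from day 43 up to and including day 394". The corresponding three-dose row covers Day 99 to Day 450, and the row for Group A3 covers Day 15 to Day 365.
- Arms with a booster get only a post-booster window. The first such row is "2-dose unvaccinated with booster: from BD-Day 1 + 14 up to and including BD-Day 181". The two other boosted Part A arms and the arm vaccinated outside the study have the same limits.

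Three other rules bear on this:

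- SAP 5.2 places everyone enrolled in Part A in the "analysis populations for Part A regardless of whether participants continue to Part B".
- The person-time rule in SAP 6.5.2 starts at the first dose of each part and can end at the dose given in the next part.
- SAP 6.5 says: "Participants with pre-booster positive or missing SARS-CoV-2 status will be excluded from the mITT Set (Part B) infection analysis".

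The derivations in SAP 6.5.1.1 to 6.5.1.5 count from 14 days after the second dose, the third dose and the booster, without regard to a later booster.

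**The concern.** The list assigns a participant's Part A window by something that happens afterwards. Take a Group A3 participant with RT-PCR-confirmed COVID-19 on Day 60 who is boosted on Day 120. The Day 15 to 365 row is labelled as without a booster, so it does not apply. The row that does apply opens on BD-Day 15. Under SAP 6.1 the Day 60 result also makes pre-booster status positive, which removes the person from the Part B infection analysis. For the four listed endpoints the case falls in no listed window, yet the person stays in the Part A mITT Set and contributes Part A person-time up to Day 120.

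If boosted and non-boosted participants are reported together, the numerator and the denominator then cover different people and the Part A rate is too low. Even if the literal list was not intended, two programmers, one following 6.5.1 and one following 6.5.2, would report different rates for the same secondary endpoints.

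**Working it through.** **1. Reproduce the plan's window starts** (last planned dose day + 14, doses on Days 29, 85 and 1).

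- Two doses: 29 + 14 = Day 43.
- Three doses: 85 + 14 = Day 99.
- Previously vaccinated: 1 + 14 = Day 15.

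All three match SAP 6.5.2. The booster start is BD-Day 1 + 14 = BD-Day 15.

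**2. Length of the uncovered Part A period** (planned booster day minus Part A window start). Booster days are from Protocol Table 10: Day 205 for Group A2, Day 120 for A3, Day 149 for the healthy Group A5. The protocol synopsis and Section 3.1.1 instead give Day 129 for the healthy group, so both are shown.

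| Group | Uncovered days | Length | Window without booster | Share |
|---|---|---|---|---|
| A2 | 99 to 204 | 205 − 99 = 106 | 450 − 99 + 1 = 352 | 30% |
| A3 | 15 to 119 | 120 − 15 = 105 | 365 − 15 + 1 = 351 | 30% |
| A5, Day 149 | 43 to 148 | 149 − 43 = 106 | 394 − 43 + 1 = 352 | 30% |
| A5, Day 129 | 43 to 128 | 129 − 43 = 86 | 352 | 24% |

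A later booster lengthens the gap. BD-Day 1 to 14 is uncounted by design and is left out.

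**3. Effect on a pooled Part A count, Group A3.** Let f be the fraction boosted, with a constant infection hazard. The documents give neither f nor a hazard. In proportion to days at risk:

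counted / true = (1 − f) × 351 / [(1 − f) × 351 + f × 105]

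- f = 50%: 175.5 / (175.5 + 52.5) = 175.5 / 228 = 77%.
- f = 80%: 70.2 / (70.2 + 84) = 70.2 / 154.2 = 46%.

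**4. Sensitivity to depletion by first infection.** Replace days with first-event probabilities, exp(−h(s − 1)) − exp(−h·e), where h is the daily hazard, s the window start and e its last day (Day 119 for boosted A3, Day 365 otherwise). Person-time is the same with or without the omitted cases, to the extent that it runs to the event or the booster for everyone, so it cancels from the ratio. At assumed hazards of 0.1 and 0.3 per person-year the A3 ratios are 0.91 and 0.90 (f = 25%), 0.76 and 0.75 (50%), 0.52 and 0.50 (75%), 0.26 and 0.25 (90%). Results for A2 and A5 (booster on Day 149) are within 0.01 of these.

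**5. Could the rows with a booster simply be the Part B windows?** That reading still leaves the Part A rows labelled as without a booster, so boosted participants would have no Part A row. SAP Appendix B, Table 3 shows what the SAP does when it intends Part A windows for boosted arms: it lists them explicitly and closes the last one at the end of Part A.

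**The case against.** The strongest reply is that the rest of the SAP points the other way. SAP 6.5.1 counts from dose 2 and dose 3 for everyone. SAP 5.2 keeps boosted participants in the Part A sets. Stopping Part A person-time at the next part's dose makes sense only if boosted people are in that analysis. The rows with a booster may have been meant as Part B windows and no more. This stands as evidence of intent. It makes the defect an internal contradiction, not a settled decision to discard cases. But nothing in the SAP ranks 6.5.1 above 6.5.2.

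Further points that stand:

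- The list omits the secondary case definition, which keeps its own rule in SAP 6.5.1.5. The Day 60 case would ordinarily qualify there. It would also be recorded as a medically attended adverse event, and Protocol 8.3.4 plans a summary of infections over the whole study.
- SAP 6.1 lets boosted and non-boosted participants be combined or analysed separately. The mismatch between cases and person-time arises only when they are combined.
- By Protocol Table 2, Group A1 has no Part B, so the two-dose row with a booster is the healthy cohort of about 20. For transplant recipients the relevant rows are those for A2 and A3, which are built the same way.
- The endpoints are secondary and descriptive. Protocol Section 8 plans no formal hypothesis test, and no primary endpoint is affected.

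**Conclusion.** The contradiction is real. For four infection endpoints, the list in SAP 6.5.2 conflicts with SAP 5.2, SAP 6.5.1 and its own person-time rule. Applied literally to pooled groups, it makes Part A counting depend on a later event and biases the rate low. The uncovered time is about 105 to 106 days per boosted participant at the planned booster days (86 for A5 under Day 129). The A3 count falls to about 77% or 46% of the true number at boosted fractions of 50% and 80%. Those percentages assume a constant hazard and fractions that are not in the documents.

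A reader might infer more than this, and the documents do not support it:

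- **That these infections are counted nowhere.** This is true of the 6.5.2 list for four endpoints, not of the SAP as a whole.
- **That Part A results come only from non-boosted people.** This describes the cases under the literal list. The denominator includes everyone.
- **That breakthrough infection in transplant recipients is understated as a matter of fact.** It is understated only if the list is followed literally and the groups are pooled.
- **That most participants will be boosted.** Amendment 4 has newly enrolled transplant recipients in A2 and A3 proceed to Part B, but the number enrolled under it is not given, and those already in Part A are only offered the booster.

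This should be fixed, but because the endpoints are secondary and descriptive it does not threaten the study's primary conclusions.

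**What to change.** In SAP 6.5.2:

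1. Give every Part A participant a Part A window regardless of later booster. Start it 14 days after the last Part A dose (Day 43, 99 or 15) and end it at the earliest of the event, the day before the booster, or the end of Part A follow-up.
2. Label the BD-Day 15 to BD-Day 181 rows as the separate Part B windows.
3. State the window for the secondary case definition, which the list omits.

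A related point does not arise from booster status. The list starts from the last planned dose, whereas the endpoint also counts from 14 days after dose 2. Group A2 therefore loses Day 43 to Day 98 (98 − 43 + 1 = 56 days) whether or not it is boosted. Reconcile the two by adding a post-dose-2 period for A2 from Day 43 to dose 3. The Day 129 and Day 149 statements for the healthy group's booster must also be reconciled in the protocol.

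The cost is SAP wording and a programming change, with no new data. Boosted participants will appear in two windows, so the tables need a label to distinguish them.

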3. If the visit for the second dose (Day 29) is disrupted and cannot be completed at Day 29 -3/+7 days as a result of the COVID-19 pandemic (self-quarantine or disruption of study site activities following business continuity plans and/or local government mandates for “stay at home” or “shelter in place”), the visit window may be extended to Day 29 + 21 days. When the extended visit window is used, the remaining clinic study visits D36 (last dose + 7 days), D57 (last dose + 28 days), 6 month visit (last dose + 180 days), and 12 month visit (last dose + 365 days) should be rescheduled to follow the scheduled inter-visit interval from the actual date of the second dose. The timing of eDiary follow-ups and safety calls will not be adjusted. Additional safety calls every 4 weeks should be scheduled if there is a gap beyond 28 days between the last safety call and the last study visit. Participants who agree to receive a booster dose in Part B of the study will follow the schedule of events for Part B (see [Table 10](#)).
4. Safety follow-up via an eDiary questionnaire will be performed every 4 weeks from Day 71 to Day 183 and again from Day 223 to Day 363.
5. Safety follow-up via a safety telephone call will be performed every 4 weeks from Day 85 to Day 197 and again from Day 237 to Day 377.
6. Physical examination: A full physical examination, including height and weight, will be performed to determine eligibility prior to administration of vaccine dose on Day 1. Body mass index will be calculated only at the screening visit (Day 0). Symptom-directed physical examinations will be performed at Day 29, Day 57, Day 209, and Day 394. Any clinically significant finding identified during a study visit should be reported as an MAAE.
7. On each injection day before injection and again 7 days after injection, the arm that received the injection should be examined and the associated lymph nodes must be evaluated. Any clinically significant finding identified during a study visit should be reported as an MAAE.

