**Table 1. Derivation for SARS-CoV-2 Infection**

Baseline SARS-CoV-2 Status	Post-baseline assessments		Endpoint: SARS-CoV-2 infection
	RT-PCR test post-baseline	bAb levels against SARS-CoV-2 Nucleocapsid	
Negative at Baseline of each part	Positive (either at scheduled NP swab test, or at symptom-prompt NP swab test 14 days after the second/third dose)		Case
Negative at Baseline of each part		Positive (28 days after the second, third dose, and BD or later) as measured by Roche Elecsys	Case

The date of documented infection will be the earlier of:

- Date of positive post-baseline RT-PCR result, or
- Date of positive post-baseline serology test result based on bAb specific to SARS-CoV-2 nucleocapsid

For Part A, the time to the first documented SARS-CoV-2 infection will be calculated as:

Time to the first SARS-CoV-2 infection = Date of the first infection – Date of first study dose + 1.

For Part B, the time to the first documented SARS-CoV-2 infection will be calculated as:

Time to the first SARS-CoV-2 infection = Date of the first infection – Date of BD + 1.

Cases will be counted starting 14 days after the second, third dose, and BD, e.g., date of documented infection - Date of the second/third dose/BD  $\geq$  14.

Confidential

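### SAP 6.5.2 stops counting infections on the nominal final-visit day, so positives from an on-schedule but later final blood draw are left out and infection rates are biased down

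*SAP*

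**What the plan says.** SAP 6.5.2 sets the case-counting period by study arm for four endpoints: any SARS-CoV-2 infection, its asymptomatic form, COVID-19 and severe COVID-19. Counting opens two weeks after the final planned dose. In the 2-dose arm that took no booster, the entry is "2-dose unvaccinated without booster: from day 43 up to and including day 394". The corresponding limits are Days 99 and 450 in the 3-dose arm and Days 15 and 365 in the previously vaccinated arm. Every boosted arm has the same form as "2-dose unvaccinated with booster: from BD-Day 1 + 14 up to and including BD-Day 181". Person-time follows a different rule. It ends at the earliest of the event date and "dose date in next part, last date of study participation, censoring time, or efficacy data cutoff date".

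SAP 6.5.1.1 to 6.5.1.5 define the cases. They set a start relative to the actual dose date ("Cases will be counted starting 14 days after the second, third dose, and BD", meaning event date minus dose date of at least 14) and no upper day. The serology criterion in 6.5.1.1 is open-ended after 28 days. In 6.5.1.2 a positive nucleocapsid result at any scheduled immunogenicity visit qualifies. A serology case is dated at the positive result.

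The protocol's schedules of events allow the final visit, with its nucleocapsid draw, within ±14 days at D394, D450 and D365 (Tables 7 to 9) and within -3/+14 days at BD-D181 (Table 10). If the extended window for a delayed dose 2 is used, later clinic visits "should be rescheduled to follow the scheduled inter-visit interval from the actual date of the second dose". Table 8 has the same rule for dose 3.

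**The concern.** The final visit can be fully compliant and still fall after the day on which 6.5.2 stops counting. A participant whose first positive nucleocapsid result comes from that draw is infected by the 6.5.1 definitions and not a case by the 6.5.2 timeframe.

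The loss is not confined to infections in the last two weeks. Scheduled swabs end at BD-D1 in Part B and 28 days after the last dose in Part A, so later silent infection is found mainly by serology. The final draw is the only scheduled one after BD-D29 in Part B and after the six-month visit in Part A. A draw one day past the close therefore drops a silent infection acquired at any time since the previous scheduled draw. The error has one direction, and it affects the stated objectives on infection incidence.

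**Working it through.** **1. Reproduce the SAP's days and extend them to the visit window.** Opening day = last planned dose day + 14. Closing day = nominal final visit. Latest on-schedule draw = closing day + upper visit allowance. Permitted days are 14 + 1 + 14 = 29 in Part A and 3 + 1 + 14 = 18 in Part B.

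| Regimen | Opens | Closes | Latest on-schedule draw | Permitted days after close |
|---|---|---|---|---|
| 2-dose, no booster | 29 + 14 = 43 | 29 + 365 = 394 | 408 | 14/29 = 48% |
| 3-dose, no booster | 85 + 14 = 99 | 85 + 365 = 450 | 464 | 14/29 = 48% |
| Previously vaccinated, no booster | 1 + 14 = 15 | 1 + 364 = 365 | 379 | 14/29 = 48% |
| Boosted arms | 1 + 14 = 15 | 1 + 180 = 181 | 195 | 14/18 = 78% |

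The SAP's opening and closing days all reproduce.

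**2. Delayed last dose.** The extension allows dose 2 up to Day 29 + 21 = 50. The 12-month visit is then Day 50 + 365 = 415 ± 14, or Days 401 to 429. All of these are after Day 394, and the last is 35 days past it. For dose 3 the figures are Day 85 + 21 = 106, then 106 + 365 = 471 ± 14, or Days 457 to 485, against a close at Day 450.

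**3. Group A3.** Table 9 labels the last visit D365 but places it 365 days after injection. By the SAP 6.1 day count (date difference + 1) that is Day 366, one day past the close with no lateness at all.

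**4. Infection time that depends on the final draw.** Days since the previous scheduled draw, over the length of the counting window:

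- 2-dose: (394 − 209)/(394 − 43 + 1) = 185/352 = 53%
- 3-dose: (450 − 265)/(450 − 99 + 1) = 185/352 = 53%
- Previously vaccinated: (365 − 180)/(365 − 15 + 1) = 185/351 = 53%
- Boosted: (181 − 29)/(181 − 15 + 1) = 152/167 = 91%

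**5. Illustrative size.** Let *s* be the share of final draws after the close and *f* the share from step 4. If infection risk is constant, seroconversion is immediate, lateness is unrelated to infection and no illness-visit serology is drawn (all assumptions), the uncounted share of serology-only infections is *s* × *f*. The documents do not give *s*, so a range is shown.

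| *s* | Part A without booster (*f* = 0.53) | Part B (*f* = 0.91) |
|---|---|---|
| 10% | 5% | 9% |
| 25% | 13% | 23% |
| 48% (A) or 78% (B): visits spread evenly over permitted days | 25% | 71% |

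**6. Denominator.** Without a dose delay, person-time past the close is at most 14 days: 14/181 = 8% in Part B, and 14/450 = 3% to 14/365 = 4% in Part A. The numerator loss is the larger part.

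**7. Other cases.** An RT-PCR case dated after the close but before the final visit is cut in the same way. The secondary COVID-19 definition is not among the four endpoints given the window, so the same event could count there and not under the main definition.

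**The case against.** The strongest reply is that the closing days are visit labels. SAP Appendix B keeps data under the nominal visit and leaves its last immunogenicity windows open (≥302, ≥358, ≥273, BD ≥106), so a Day 400 draw is analysed there as the Day 394 visit. SAP 6.5.1.1 also uses day numbers as labels. But Appendix B is limited to safety and immunogenicity, 6.5.2 does not refer to it, and Day 43 and BD-Day 1 + 14 match no visit. The limits read as day arithmetic. If labels were meant, the SAP needs to say so.

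Several other replies do stand:

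- SAP 6.5.1 sets the case definition and start; it does not forbid a stop in 6.5.2. This is a restriction that discards qualifying cases, not a direct contradiction.
- The fixed lower limits might suggest that infections before a delayed dose, or soon after it, are counted. The actual-dose rule in 6.5.1 excludes them.
- Nucleocapsid serology is also drawn at illness and convalescent visits, and close contact prompts a swab. The final draw is the last scheduled one, not the only later one.
- The person-time rule includes an undefined censoring time, which might be set at the close.
- Late positives should still appear in the by-visit serology summaries (SAP 6.5) and in the whole-study counts of protocol 8.3.4.

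**Conclusion.** The point holds and is moderate. Applied as written, SAP 6.5.2 omits infections first detected at a compliant final draw 1 to 14 days after the close, or up to 35 days after it when the last dose was delayed under the extension. For Group A3 the days-since-injection schedule is itself one day past the close. Rates of SARS-CoV-2 infection and asymptomatic infection are biased down, with more exposure in Part B.

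A reader might take the 48% and 78% of permitted days, or the last row of the table in step 5, as the expected loss. The documents do not support that. They give no distribution of visit days, visits may cluster on the target day, and the table covers serology-only infections, not all infections. The Part A limits also apply only to participants without a booster, while Groups A2, A3 and A5 are offered one.

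Nor does this reach the main conclusions. The affected rates are descriptive, secondary in Part A and exploratory in Part B. No hypothesis test, primary endpoint or sample size depends on them.

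**What to change.** In SAP 6.5.2, replace the fixed study-day limits with a rule on actual dates. Count cases from 14 days after the actual date of the last planned dose or BD for RT-PCR, or 28 days after it for serology (subject to the visit window, so that an early but in-window 28-day draw still qualifies). Continue through the earliest of the dose date in the next part, the last date of study participation including the final visit, or the data cutoff. Use the same stop rule for cases and person-time, and either define the censoring time or remove it. State whether the timeframe also applies to the secondary COVID-19 definition. For the lower limits, a sentence saying that the actual-dose rule in 6.5.1 governs is enough.

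The cost is SAP wording and one derivation. No new data are needed. It should be settled before database lock.
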